## 8.2.4. Hospitalization

Hospitalization is defined as any initial admission (even less than 24 hours) in a hospital or equivalent healthcare facility, or any prolongation of an existing admission. Admission also includes transfer within the hospital to an acute/intensive care unit (eg, from the psychiatric wing to a medical floor, medical floor to a coronary care unit, or neurological floor to a tuberculosis unit). An emergency room visit does not necessarily constitute a hospitalization; however, the event leading to the emergency room visit is assessed for medical importance.

Hospitalization does not include the following:

- Rehabilitation facilities;
- Hospice facilities;
- Respite care (eg, caregiver relief);
- Skilled nursing facilities;
- Nursing homes;
- Same-day surgeries (as outpatient/same-day/ambulatory procedures).

Hospitalization or prolongation of hospitalization in the absence of a precipitating clinical AE is not in itself an SAE. Examples include:

- Admission for treatment of a preexisting condition not associated with the development of a new AE or with a worsening of the preexisting condition (eg, for workup of a persistent pretreatment laboratory abnormality);
- Social admission (eg, patient has no place to sleep);
- Administrative admission (eg, for yearly physical examination);
- Protocol-specified admission during a study (eg, for a procedure required by the study protocol);
- Optional admission not associated with a precipitating clinical AE (eg, for elective cosmetic surgery);
- Hospitalization for observation without a medical AE;
- Preplanned treatments or surgical procedures. These should be noted in the baseline documentation for the entire protocol and/or for the individual patient;
- Admission exclusively for the administration of blood products.

Diagnostic and therapeutic noninvasive and invasive procedures, such as surgery, should not be reported as SAEs. However, the medical condition for which the procedure was performed should be reported if it meets the definition of an SAE. For example, an acute appendicitis that begins during the reporting period should be reported if the SAE requirements are met, and the resulting appendectomy should be recorded as treatment of the AE.

GRADE	Clinical Description of Severity
0	No change from normal or reference range (This grade is not included in the Version 4.03 CTCAE document but may be used in certain circumstances.)
1	MILD adverse event
2	MODERATE adverse event
3	SEVERE adverse event
4	LIFE-THREATENING consequences; urgent intervention indicated
5	DEATH RELATED TO adverse event

#### 8.3. Severity Assessment

Note the distinction between the severity and the seriousness of an AE. A severe event is not necessarily an SAE. For example, a headache may be severe (interferes significantly with the patient's usual function) but would not be classified as serious unless it met one of the criteria for SAEs, listed above.

#### 8.4. Special Situations

## 8.4.1. Potential Cases of Drug-Induced Liver Injury

Humans exposed to a drug who show no sign of liver injury (as determined by elevations in transaminases) are termed "tolerators," while those who show transient liver injury, but adapt are termed "adaptors." In some patients, transaminase elevations are a harbinger of a more serious potential outcome. These patients fail to adapt and therefore are "susceptible" to progressive and serious liver injury, commonly referred to as drug-induced liver injury (DILI). Patients who experience a transaminase elevation above 3 times the upper limit of normal (× ULN) should be monitored more frequently to determine if they are an "adaptor" or are "susceptible."

In the majority of DILI cases, elevations in aspartate aminotransferase (AST) and/or alanine aminotransferase (ALT) precede total bilirubin (TBili) elevations (>2 × ULN) by several days or weeks. The increase in TBili typically occurs while AST/ALT is/are still elevated above  $3 \times ULN$  (ie, AST/ALT and TBili values will be elevated within the same lab sample). In rare instances, by the time TBili elevations are detected, AST/ALT values might have decreased. This occurrence is still regarded as a potential DILI. Therefore, abnormal elevations in either AST OR ALT in addition to TBili that meet the criteria outlined below are considered potential DILI (assessed per Hy's law criteria) cases and should always be considered important medical events, even before all other possible causes of liver injury have been excluded. The threshold of laboratory abnormalities for a potential DILI case depends on the patient's individual baseline values and underlying conditions. Patients who present with the following laboratory abnormalities should be evaluated further as potential DILI (Hy's law) cases to definitively determine the etiology of the abnormal laboratory values:

- Patients with AST/ALT and TBili baseline values within the normal range who subsequently present with AST OR ALT values >3 × ULN AND a TBili value >2 × ULN with no evidence of hemolysis and an alkaline phosphatase value <2 × ULN or not available;
- For patients with baseline AST **OR** ALT **OR** TBili values above the ULN, the following threshold values are used in the definition mentioned above, as needed, depending on which values are above the ULN at baseline:
  - Preexisting AST or ALT baseline values above the normal range: AST or ALT values >2 times the baseline values AND >3 × ULN; or >8 × ULN (whichever is smaller).
  - Preexisting values of TBili above the normal range: TBili level increased from baseline value by an amount of at least 1 × ULN or if the value reaches >3 × ULN (whichever is smaller).

Rises in AST/ALT and TBili separated by more than a few weeks should be assessed individually based on clinical judgment; any case where uncertainty remains as to whether it represents a potential Hy's law case should be reviewed with the sponsor.

The patient should return to the investigator site and be evaluated as soon as possible, preferably within 48 hours from awareness of the abnormal results. This evaluation should include laboratory tests, detailed history, and physical assessment.

In addition to repeating measurements of AST and ALT and TBili, laboratory tests should include albumin, creatine kinase (CK), direct and indirect bilirubin, gamma-glutamyl transferase (GGT), prothrombin time (PT)/international normalized ratio (INR), total bile acids, alkaline phosphatase and acetaminophen drug and/or protein adduct levels. Consideration should also be given to drawing a separate tube of clotted blood and an anticoagulated tube of blood for further testing, as needed, for further contemporaneous analyses at the time of the recognized initial abnormalities to determine etiology. A detailed history, including relevant information, such as review of ethanol, acetaminophen (either by itself or as a coformulated product in prescription or over-the-counter medications), recreational drug, supplement (herbal) use and consumption, family history, sexual history, travel history, history of contact with a jaundiced person, surgery, blood transfusion, history of liver or allergic disease, and potential occupational exposure to chemicals, should be collected. Further testing for acute hepatitis A, B, C, D, and E infection and liver imaging (eg, biliary tract) may be warranted. All cases demonstrated on repeat testing as meeting the laboratory criteria of AST/ALT and TBili elevation defined above should be considered potential DILI (Hy's law) cases if no other reason for the liver function test (LFT) abnormalities has yet been found. Such potential DILI (Hy's law) cases are to be reported as SAEs, irrespective of availability of all the results of the investigations performed to determine etiology of the LFT abnormalities.

A potential DILI (Hy's law) case becomes a confirmed case only after all results of reasonable investigations have been received and have excluded an alternative etiology.

# **8.4.2.** Exposure to the Lorlatinib During Pregnancy or Breastfeeding, and Occupational Exposure

Exposure to lorlatinib under study during pregnancy or breastfeeding and occupational exposure are reportable to Pfizer Safety within 24 hours of investigator awareness.

# 8.4.2.1. Exposure During Pregnancy

For both unapproved/unlicensed products and for marketed products, an EDP occurs if:

- A female becomes, or is found to be, pregnant either while receiving or having been exposed (eg, because of treatment or environmental exposure) to lorlatinib; or the female becomes or is found to be pregnant after discontinuing and/or being exposed to lorlatinib;
  - An example of environmental exposure would be a case involving direct contact with a Pfizer product in a pregnant woman (eg, a nurse reports that she is pregnant and has been exposed to chemotherapeutic products).
- A male has been exposed (eg, because of treatment or environmental exposure) to lorlatinib prior to or around the time of conception and/or is exposed during his partner's pregnancy.

If a patient or patient's partner becomes or is found to be pregnant during the patient's treatment with lorlatinib, the investigator must report this information to Pfizer Safety on the CT SAE Report Form and an EDP supplemental form, regardless of whether an SAE has occurred. In addition, the investigator must submit information regarding environmental exposure to a Pfizer product in a pregnant woman (eg, a patient reports that she is pregnant and has been exposed to a cytotoxic product by inhalation or spillage) to Pfizer Safety using the EDP supplemental form. This must be done irrespective of whether an AE has occurred and within 24 hours of awareness of the exposure. The information submitted should include the anticipated date of delivery (see below for information related to termination of pregnancy).

Follow-up is conducted to obtain general information on the pregnancy and its outcome for all EDP reports with an unknown outcome. The investigator will follow the pregnancy until completion (or until pregnancy termination) and notify Pfizer Safety of the outcome as a follow-up to the initial EDP supplemental form. In the case of a live birth, the structural integrity of the neonate can be assessed at the time of birth. In the event of a termination, the reason(s) for terminated fetus should be assessed by gross visual inspection (unless pre-procedure test findings are conclusive for a congenital anomaly and the findings are reported).

If the outcome of the pregnancy meets the criteria for an SAE (ie, ectopic pregnancy, spontaneous abortion, intrauterine fetal demise, neonatal death, or congenital anomaly [in a live-born baby, a terminated fetus, an intrauterine fetal demise, or a neonatal death]), the investigator should follow the procedures for reporting SAEs.

Additional information about pregnancy outcomes that are reported to Pfizer Safety as SAEs follows:

- Spontaneous abortion includes miscarriage and missed abortion;
- Neonatal deaths that occur within 1 month of birth should be reported, without regard to causality, as SAEs. In addition, infant deaths after 1 month should be reported as SAEs when the investigator assesses the infant death as related or possibly related to exposure to lorlatinib.

Additional information regarding the EDP may be requested by the sponsor. Further follow-up of birth outcomes will be handled on a case-by-case basis (eg, follow-up on preterm infants to identify developmental delays). In the case of paternal exposure, the investigator will provide the patient with the Pregnant Partner Release of Information Form to deliver to his partner. The investigator must document in the source documents that the patient was given the Pregnant Partner Release of Information Form to provide to his partner.

# 8.4.2.2. Exposure During Breastfeeding

Scenarios of exposure during breastfeeding must be reported, irrespective of the presence of an associated SAE, to Pfizer Safety within 24 hours of the investigator's awareness, using the CT SAE Report Form. An exposure during breastfeeding report is not created when a Pfizer drug specifically approved for use in breastfeeding women (eg, vitamins) is administered in accord with authorized use. However, if the infant experiences an SAE associated with such a drug's administration, the SAE is reported together with the exposure during breastfeeding.

# 8.4.2.3. Occupational Exposure

An occupational exposure occurs when, during the performance of job duties, a person (whether a healthcare professional or otherwise) gets in unplanned direct contact with the product, which may or may not lead to the occurrence of an AE.

An occupational exposure is reported to Pfizer Safety within 24 hours of the investigator's awareness, using the CT SAE Report Form, regardless of whether there is an associated SAE. Since the information does not pertain to a patient enrolled in the study, the information is not recorded on a CRF; however, a copy of the completed CT SAE Report Form is maintained in the investigator site file.

## 8.4.3. Medication Errors and Lack of Efficacy

Other exposures to lorlatinib under study may occur in clinical trial settings, such as medication errors and lack of efficacy.

Safety Event	Recorded on the CRF	Reported on the CT SAE Report Form to Pfizer Safety Within 24 Hours of Awareness
Medication errors and lack of efficacy*	All (regardless of whether associated with an AE)	Only if associated with an SAE

\*For lack of efficacy (particularly for studies conducted with vaccines, contraceptives, and products used in the treatment of life-threatening diseases or conditions [eg, anti-infectives]), see the Lack of Efficacy section below.

## 8.4.3.1. Medication Errors

Medication errors may result from the administration or consumption of lorlatinib by the wrong patient, or at the wrong time, or at the wrong dosage strength. Medication errors include:

- Medication errors involving patient exposure to lorlatinib;
- Potential medication errors or uses outside of what is foreseen in the protocol that do or do not involve the participating patient.

Such medication errors occurring to a study participant are to be captured on the medication error page of the CRF, which is a specific version of the AE page.

In the event of medication dosing error, the sponsor should be notified immediately.

Whether or not the medication error is accompanied by an AE, as determined by the investigator, the medication error is recorded on the medication error page of the CRF and, if applicable, any associated AE(s), serious and non-serious, are recorded on an AE page of the CRF.

Medication errors should be reported to Pfizer Safety within 24 hours on a CT SAE Report Form only when associated with an SAE.

## 8.4.3.2. Lack of Efficacy

Lack of efficacy in an approved indication should be reported as an SAE to Pfizer Safety.

Lack of efficacy is reportable to Pfizer Safety only if associated with an SAE.

# 9. DATA ANALYSIS/STATISTICAL METHODS

Detailed methodology for summary and statistical analyses of the data collected in this study is outlined here and further detailed in a statistical analysis plan (SAP), which will be maintained by the sponsor. The SAP may modify what is outlined in the protocol where appropriate; however, any major modifications of the primary endpoint definitions or their analyses will also be reflected in a protocol amendment.

## 9.1. Analysis Sets

1. Safety analysis set:

The safety analysis set includes all enrolled patients who receive at least one dose of lorlatinib.

2. Full analysis set:

The full analysis set includes all enrolled patients.

3. PK analysis sets:

The PK concentration population is defined as all enrolled patients who are treated and have at least 1 analyte concentration.

The PK parameter analysis population is defined as all enrolled patients treated who have sufficient information to estimate at least 1 of the PK parameters of interest.

The PK evaluable analysis population is defined as all patients in the PK parameter analysis population who have (1) completed Cycle 2 Day 1 PK collection; (2) received lorlatinib dose on Cycle 2 day 1; (3) received at least 80% of total dose within 14 days prior to Cycle 2 Day 1; (4) no dose reduction in the first cycle.

4. Response Evaluable set – includes all patients in the safety analysis population who have an adequate baseline tumor assessment.

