 $R_{ac}$  is the observed accumulation ratio calculated by Day 15 AUCtau/Lead In Day -7 AUCtau or Day 1 AUCtau. Rss is the steady state accumulation ratio calculated by Day 15 AUCtau/Lead In Day -7 AUCinf.

After single oral administration of the acetate solvate form of lorlatinib under fasted conditions, median peak plasma concentrations were observed between 1 and 2 hours. Following attainment of  $C_{max}$ , lorlatinib plasma concentrations showed a bi-exponential decline with mean terminal elimination half-life ranging across the tested dose groups from 17.2 to 27.2 hours, mean apparent oral clearance (CL/F) of 9.8 to 15.8 L/hr and mean volume of distribution (Vz/F) of 308 to 410 L. Variability in PK was observed with a coefficient of variation (CV%) of 25-79% across tested doses for AUCinf and 17-45% for Cmax following single oral administration.

After repeated QD oral administration, steady state should have been achieved before Day 15 based on the lorlatinib apparent terminal elimination half-life (Table 3). The observed steady state accumulation rations ( $R_{ac}$  and  $R_{ss}$ , respectively) seemed to be less than the predicted values based on the calculated lorlatinib elimination rate and the frequency of administration, which suggests auto-induction may play a role in lorlatinib disposition. The auto-induction seems more prominant with increasing dose levels, as the observed accumulation index becomes smaller.

PK data (March 2017) after 100 mg single and multiple dosing in Phase 1 with acetate solvate drug form and in Phase 2 with free base drug form are summarized in Table 3.

Dose	Ν	AUC (ng•hr/mL)	C max (ng/mL)	T max (hr)	t 1/2 (hr)	CL/F (L/hr)	V z /F (L)
Phase 1: Acetate	Solvate			 			
Single Dose	16	8236 (25)	595.5 (37)	1.96 (0.517-4.33)	20.9±5.03	12.14 (25)	356.3 (39)
Multiple Doses	16	5121 (30)	550.2 (32)	1.13 (1.0-4.0)	NA	19.52 (30)	NA
Phase 2: Free Ba	se						
Single Dose	19	9088 (35)	695.2 (40)	1.55 (0.50-4.02)	23.6±9.37	11.01 (35)	351.5 (37)
Multiple Doses	26	5650 (39)	576.5 (42)	1.96 (0.50-22.7)	NA	17.70 (39)	NA

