- Groups A1 and A2 (Normal): patients with normal liver function will be included in this study as matching control patients (Group A1 for Group B and Group A2 for Group C). If the dose for moderate hepatic impairment group (Group C) is selected to be the recommended clinical dose of 100 mg QD, the control group A2 will not be needed to be enrolled. There will be no control group designated to match severe group. However, if a decision has been made to use the same dose for severe and moderate patients, the half of the control Group A2 will be matching Group C and half will be matching Group D.

Child-Pugh scores (criteria listed in Appendix 3) will be calculated and recorded as part of the liver function testing prior to the start of the first lorlatinib dose, but will not be used to stratify patients into treatment groups.

The enrollment of approximately 76 advanced cancer patients is anticipated in this study in order to have 8 PK-evaluable patients in each of Groups A1, A2, B and C, and 6 PK-evaluable patients in Group D for final statistical analysis. Evaluable patients are those who complete the planned PK sample collection on Cycle 2 Day 1 and have no lorlatinib dose modification until completion of Cycle 2 Day 1 PK evaluation. Patients who are not evaluable for PK will be replaced.

Each patient will be treated with repeated oral once daily doses of lorlatinib in 21-day cycles until disease progression, patient refusal, or unacceptable toxicity occurs.

The planned dosing schedule for each treatment group is as follows (Table 4):

	Group B	Group C	Group D	Group A1	Group A2
Hepatic Function	Mild	Moderate	Severe	Normal	Normal
Starting Lorlatinib Dose	100 mg QD	50 mg QD or otherwise determined in the first stage	determined based on preliminary safety and PK data	100 mg QD	the same dose as Group C at the second stage
Lorlatinib Dose After PK Assessment	100 mg QD	50 mg QD or otherwise determined in the first stage	determined based on preliminary safety and PK data	100 mg QD	100 mg QD

Table 4.Lorlatinib Dosing Schedule

The dose schedule may be modified as necessary for individual patients according to tolerability (see Table 6 for detailed dose modification strategy).

For Group C, a two-stage enrollment will be applied.

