## 5.9.7. Concomitant Radiotherapy

Palliative radiotherapy to specific sites of disease is permitted if considered medically necessary by the treating physician. All attempts should be made to rule out disease progression in the event of increased localized pain. If palliative radiotherapy is needed to control bone pain, the sites of bone disease should be present at baseline, otherwise, bone pain requiring radiotherapy will be considered as a sign of disease progression.

Lorlatinib must be stopped 24 hours before and at least 24 hours after completion of radiation therapy. In view of the current lack of data about the interaction of lorlatinib with radiotherapy, lorlatinib treatment should be interrupted during palliative radiotherapy, stopping 1 day before and resuming treatment after recovery from acute radiation toxicities to baseline.

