3. ENDPOINTS AND BASELINE VARIABLES: DEFINITIONS AND CONVENTIONS

3.1. Primary Endpoint(s)

Plasma PK parameters of lorlatinib at steady state: AUC₂₄ and C_{max}.

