3.4.2.2. PK Parameter Analysis Set

The PK parameter analysis set is defined as all enrolled patients treated who have sufficient information to estimate at least 1 of the PK parameters of interest.

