One-way analysis of variance (ANOVA) will be used to compare the natural log transformed AUC_{24} , AUC_{last} and C_{max} of lorlatinib at steady state for each of the hepatic impairment groups (Test) to the corresponding normal hepatic function group with the same dosing schedule (Reference). Group B (Test) will be compared to Group A1 (Reference) and Group C (Test) will be compared with Group A2 (Reference). If a decision has been made to use the same dose for severe and moderate patients, the half of the control Group A2 will be matching Group C and half will be matching Group D (test), and the corresponding pairwise comparisons will be made. Additionally, Group D will be compared to Group A1 (Reference), and Group C will be compared with A1. Estimates of the mean differences (Test-Reference) and corresponding 90% confidence intervals will be obtained from the

model. The mean differences and 90% confidence intervals for the differences will be exponentiated to provide estimates of the ratio of geometric means (Test/Reference) and 90% confidence intervals for the ratios.

Residuals from the models will be examined for normality and the presence of outliers via visual inspection of plots of residuals vs predicted values and normal probability plots of residuals but these will not be included in the clinical study report. If there are major deviations from normality or outliers then the effect of these on the conclusions will be investigated through alternative transformations and/or analyses excluding outliers. Justification for any alternative to the planned analysis will be given in the report of the study.

The following PK parameters will be summarized descriptively by analyte, hepatic function group and at C1D1 and C2D1 for lorlatinib and its metabolites.

| Parameter | Summary statistics |
|--|--|
| AUC _{24,} AUC _{last} , C _{max} , C _{min} , CL/F, MRAUC _{24,} MRAUC _{last} , MRC _{max} | N, arithmetic mean, median, cv%, standard deviation, minimum, maximum, geometric mean. |
| T _{max} | N, median, minimum, maximum. |

Box and whisker plots for individual subject parameters (lorlatinib AUC $_{24}$, AUC_{last} and C_{max}) will be presented against hepatic function group by analyte and overlaid with geometric means.

PK parameter analysis set will be used for performing the analysis.

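### The 80%-of-dose rule for PK evaluability ignores when doses were missed, so a Cycle 2 Day 1 profile that is not at steady state can count as evaluable, and the primary ANOVA set has no adherence condition either

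*Protocol*

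**What the plan says.** The primary endpoint is AUC24 and Cmax, described as "Plasma PK parameters of lorlatinib at steady state" (SAP 3.1) and taken from the Cycle 2 Day 1 profile. Three places bear on who contributes to it, and they differ.

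- **Protocol 9.1 and SAP 3.4.2.3** (PK evaluable set): Cycle 2 Day 1 sampling completed, dose taken that day, "received at least 80% of total dose within 14 days prior to Cycle 2 Day 1", and no dose reduction in Cycle 1. Nothing says which days may be missed.
- **Protocol 3.1**, repeated in SAP 2.2: evaluable patients complete the sampling and "have no lorlatinib dose modification until completion of Cycle 2 Day 1 PK evaluation". There is no 80% threshold.
- **SAP 5.1.1.1**, after describing the ANOVA: "PK parameter analysis set will be used for performing the analysis". That set needs only "sufficient information to estimate at least 1 of the PK parameters of interest" (SAP 3.4.2.2), with no condition on adherence.

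PK evaluability therefore decides who is counted and replaced (Protocol 3.1 and 9.2). It also decides which 3 Group C patients inform the dose decision for the later patients (Protocol 3.1, SAP 6). Under the SAP it does not decide who enters the primary ANOVA; Protocol 9.3.3 names no set.

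**The concern.** Steady-state exposure depends on the most recent doses. A sum over 14 days scores a gap on Days 8 and 9 the same as a gap on Days 20 and 21, although the first has washed out by Day 22 and the second has not. A patient with the second pattern who takes the Cycle 2 Day 1 dose meets all four criteria, because an interruption is not a reduction.

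The protocol provides for such gaps. Missed doses may be skipped and are recorded (5.4), and for palliative radiotherapy "Lorlatinib must be stopped 24 hours before and at least 24 hours after completion of radiation therapy" (5.9.7). With 8 evaluable patients per group, 6 in Group D and 3 in Group C stage 1, a single low profile carries weight in the group geometric mean.

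**Working it through.** **1. The plan's own figures.** The evaluable total reproduces: 4 × 8 + 6 = 38. So does clearance at 100 mg, as Dose/AUC from Protocol Table 3: 100,000/5650 = 17.70 L/h (Phase 2, multiple dose) and 100,000/8236 = 12.14 L/h (Phase 1, single dose). The documents give no figure for AUC lost after missed doses.

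**2. What the rule accepts.** The 14 once-daily doses fall on Days 8-21. Two missed: 12/14 = 85.7%, passes. Three missed: 11/14 = 78.6%, fails.

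**3. One-compartment shortfall.** By superposition, with r = exp(-ln2 × 24/t½), the dose taken k days earlier supplies (1 - r)r^k of a steady-state AUC24. Missing the last m doses costs r(1 - r^m). Induced half-lives are ln2 × (Vz/F)/(CL/F) from Table 3: 0.693 × 351.5/17.70 = 13.8 h (Phase 2) and 0.693 × 356.3/19.52 = 12.7 h (Phase 1).

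| Half-life | Source | Last dose missed | Last two missed |
|---|---|---|---|
| 12.7 h | Phase 1, induced | 19.6% | 24.9% |
| 13.8 h | Phase 2, induced | 21.0% | 27.2% |
| 20.9 h | Phase 1, single dose | 24.8% | 35.9% |
| 23.6 h | Phase 2, single dose | 25.0% | 37.3% |

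The Phase 2 inputs give 27-37%. Missing Days 8 and 9 instead costs under 0.01%. Averaged over every possible pair of missed days, the loss is 4-7%, so the last pair is the worst case.

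**4. Allowing for the curve shape and induction.** The protocol reports a "bi-exponential decline with mean terminal elimination half-life ranging across the tested dose groups from 17.2 to 27.2 hours" and accumulation below prediction, "which suggests auto-induction may play a role in lorlatinib disposition". Both reduce carry-over. From Table 1, the share of a single-dose AUC falling after 24 h is 1 - 5110/8236 = 0.380, against 0.451 in the one-compartment model at 20.9 h. This gives 0.380 × (1 - 0.451²) = 30%. A two-compartment model (absorption rate of 2/h assumed) matched to the single-dose half-life, Cmax and that 38% share also gives 30% at single-dose clearance. At the steady-state clearances it gives 23% (17.70 L/h) and 21% (19.52 L/h). The range for one patient is therefore about 21-37%.

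**5. Group level.** The fall in the geometric mean from one affected patient in n is 1 - (1 - loss)^(1/n).

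| Loss in the patient | 1 of 8 | 2 of 8 | 1 of 6 | 1 of 3 |
|---|---|---|---|---|
| 21% | 2.9% | 5.7% | 3.9% | 7.6% |
| 27% | 3.9% | 7.6% | 5.1% | 10.0% |
| 37% | 5.6% | 10.9% | 7.4% | 14.3% |

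**6. Which set matters.** The PK evaluable set is a subset of the PK parameter set, so this patient enters the ANOVA under either. So, by definition, does one who missed the last three doses and fails the 80% rule (one-compartment shortfall 26-44%).

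**7. Length of a protective window.** 5 × 23.6 h = 118 h, about 5 days. If Days 17-21 must all be taken, the worst remaining pair is Days 15 and 16, costing r^6(1 - r²). At 23.6 h, r = 0.494 and the loss is 0.0146 × 0.756 = 1.1%.

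**The case against.** The strongest reply is that the 80% rule does not govern the primary estimate at all, since the SAP runs the ANOVA on another set. That is right. It defeats the reading that the rule by itself biases the primary result, and it means that editing Protocol 9.1 and SAP 3.4.2.3 alone would leave these patients in the ANOVA. It does not protect the estimate, because the set actually used is looser still.

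Second, safeguards exist. SAP 4.3.2 drops a parameter known to be biased by an unexpected event, SAP 5.4.2.2 allows exclusion for poor dosing compliance, and SAP 5.1.1.2 plots predose concentrations to judge steady state. Protocol 3.1 bars dose modification, and two consecutive missed days meet the SAP 5.4.3 definition of an interruption. These help, but none settles the case. The first gives vomiting as its example and no test for missed doses; the second is discretionary and has no threshold; the plots trigger no exclusion; and Protocol 3.1 differs from 9.1 and does not clearly reach forgotten doses.

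Third, the effect is small beside the study's imprecision. With the CVs of 30-39% in Table 3, the log-scale SD is √ln(1 + CV²) = 0.294-0.376. An 8-versus-8 comparison (14 df, t = 1.761, standard error SD × √(2/8)) has a 90% interval around a ratio of 1 of 0.77-1.30 to 0.72-1.39. The study is expressly unpowered (SAP 4.1). This stands and limits the weight of the point.

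A reader might also infer that the ratio is pulled downward because impaired patients miss more doses. No section says they do. Controls are also advanced-cancer patients under the same eligibility criteria, and equal gaps would partly cancel. Nor does a longer half-life always enlarge the loss: for two missed doses it peaks at 38.5% near 30 h, then falls to 37% at 40 h and 32% at 60 h.

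**Conclusion.** The point holds in a limited form. The evaluability rule is blind to timing and accepts a profile whose AUC24 is about 21-37% below steady state. That is a worst-case figure for one patient, not an error in the group mean or ratio: all 8 patients would have to be affected to move a group of 8 that far. One affected patient shifts a group of 8 by about 3-6%. The rule matters most directly in Group C stage 1, where it selects the 3 patients reviewed and one affected patient shifts the geometric mean by about 8-14%. The direction of any net bias between groups is not documented.

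The sizes assume linear kinetics over the gap, no loss of induction within 48 hours and an unchanged volume at steady state. The half-life in hepatic impairment is not given, and the frequency of late missed doses is unknown. Cmax would also fall through lost carry-over, but was not quantified here. This is a low-cost improvement, not a defect that invalidates the analysis.

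**What to change.** (a) In SAP 5.1.1.1, add a sensitivity ANOVA of steady-state AUC24 and Cmax that excludes patients who missed any scheduled lorlatinib dose in the 5 days before Cycle 2 Day 1. Identify and flag the same patients in the Group C stage 1 PK review (SAP 6). This works whichever set serves the primary analysis and uses the diary and tablet counts already collected (Protocol 5.2 and 5.4).

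(b) Reconcile the evaluability wording in Protocol 3.1 with Protocol 9.1 and SAP 3.4.2.3, and both with the set named in SAP 5.1.1.1, so that one named set serves the primary ANOVA. If the sponsor accepts replacing a few more patients, apply the timing condition to that set.

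The cost of (a) is a short SAP addition and one extra run on slightly fewer patients. The cost of (b) is a wording change in both documents and, if the condition is adopted, some further replacements or a slightly smaller analysis set.
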